IMP	Investigational Medicinal Product	
IMV	Invasive Mechanical Ventilation	
ISF	Investigator Site File	

ISRCTN	International Standard Randomised Controlled Trials Number	
LOS	Length of Stay	
MHRA	Medicines and Healthcare products Regulatory Agency	
NHS	National Health Service	
NICE	National Institute for Health and Care Excellence	
NIV	Non-Invasive Ventilation	
PI	Principal Investigator	
PSA	Probabilistic Sensitivity Analysis	
PSS	Personal Social Services	
QA	Quality Assurance	
QALY	Quality Adjusted Life Year	
REC	Research Ethics Committee	
SAE	Serious Adverse Event	
SAR	Serious Adverse Reaction	
SDV	Source Data Verification	
SPC	Summary of Product Characteristics	
SoC	Standard of Care	
SOP	Standard Operating Procedure	
SUSAR	Suspected Unexpected Serious Adverse Reaction	
TMF	Trial Master File	
TMG	Trial Management Group	
TSC	Trial Steering Committee	
UK	United Kingdom	

TRIAL SUMMARY

Trial Title	Glu cocorticoids in adults with A cute R espiratory D istress S yndrome: A randomised, parallel-group, allocation- concealed, open label, pragmatic, group sequential design, clinical and cost- effectiveness trial with internal pilot
Study Acronym	GuARDS Trial
Clinical Phase	Phase IV
Trial Design	Randomised, parallel-group, allocation-concealed, open label, pragmatic, group sequential design
Trial Participants	1708
Planned Number of Participants	1708
Planned Number of Sites	At least 60
Countries Anticipated to be Involved in Trial	All 4 UK Home Nations (England, Wales, Northern Ireland, and Scotland)
Treatment Duration	10 days
Follow up Duration	180 days
Total Planned Trial Duration	60 months
Primary Objective	To determine the clinical effectiveness of dexamethasone on the primary outcome of 60-day mortality,
Secondary Objectives	To determine the clinical effectiveness of dexamethasone in moderate to severe ARDS To assess the cost-efficiency of dexamethasone plus usual care versus usual care alone in the treatment of ARDS, as per NICE reference case specifications modelled over 1, 3, and 5 year, and lifetime time horizons.
Primary Endpoint	All-cause mortality at 60-days from randomisation
	In hospital Extubation; Re-intubation; Duration of stay in intensive care unit from randomisation; duration of stay in hospital from randomisation At 60 days Health-related quality of life; Health Service Use Follow-up
Secondary Endpoint	At 90 days All-cause mortality; Health-related quality of life; Health Service Use Follow-up
	At 180-days All-cause mortality; Health-related quality of life; Health Service Use Follow-up
IMP(s)	Dexamethasone
IMP Route of Administration	Intravenous

Background to the trial:

Every year about 120,000 adults who are admitted to Intensive Care Units (ICUs) require a machine, called a ventilator, to help them breathe. In patients who need ventilation, about 1 in 4 have a life-threatening condition with severe breathing difficulties called acute respiratory distress syndrome (ARDS). Unfortunately, around 40% of patients with ARDS die within 60 days of developing this condition.

Breathing difficulties in ARDS happen because the lungs fill with fluid due to inflammation, which is part of the body's response to the conditions causing ARDS. Over the last 30-years, various drug treatments have been tested to reduce the inflammation in ARDS, with little success. At present, there are no drugs that cure ARDS. However, in 2020, a small research study (the DEXA-ARDS trial) in Spain looked at dexamethasone as a treatment for ARDS.

Dexamethasone is a well-known steroid, which is a cheap antiinflammatory drug that is already widely used to treat other illnesses (such as arthritis and asthma). The result of DEXA-ARDS trial showed that it may help patients survive ARDS. These results from Spain are hopeful but to help us know how effective dexamethasone is, we need to test it in a much larger group of patients who come into the NHS with ARDS. We are planning to conduct a large clinical trial across the UK.

Lay Summary of Trial

Aim(s) of the trial:

The aims of our study is to find out if dexamethasone treatment in patients with ARDS can save lives, reduce the need for extended ICU care, improve longer term patient quality of life and find the best value for the public and health services.

Design:

The study design is called a randomised controlled trial (RCT). We plan to recruit up to 1708 adult patients with ARDS, in approximately 60 ICUs throughout the UK. We will ask patients, or their Legal Representatives if patients are unable to make decisions about their care, to agree (consent) to take part in our study. We will also ask patients if we could follow them up for 6 months after their treatment, as this will give us important information about the clinical effectiveness and cost effectiveness of the treatment. Patients who agree to take part in the trial will then be assigned at random to either dexamethasone in addition to the usual intensive care (intervention), or to usual intensive care only (control), for up to 10 days or until critical care (ICU/HDU) discharge day, whichever occurs first. We will not change other regular care provided in the NHS. The main outcome of the study is whether dexamethasone improves survival at 60-days compared with usual care. This study will be open labelled meaning that the healthcare practitioners and patients will know which group of the study they have been allocated to. Blinding is not appropriate in this case as commonly

seen side effects of dexamethasone, such as reduced inflammatory markers and raised blood sugar, would point to which group the patient was in.

Patient and public involvement (PPI):

Patients, carers and family are an important part of our team and they have helped us establish the need for this research and to write the study protocol. Their experiences and advice also help us to design and ethically conduct the trial. They will continue to be central in the ongoing delivery and reporting of the study.

1. INTRODUCTION

1.1 BACKGROUND

1.1.1 Acute Respiratory Distress syndrome (ARDS)

ARDS is an acute diffuse, inflammatory lung injury. There are several aetiologies that cause ARDS, including pneumonia, non-pulmonary infections, acute pancreatitis, trauma, transfusions, burns, aspiration pneumonitis, and sepsis. The resulting injury affects the resident immune cells, and alveolar capillary membrane. There is an influx of circulating immune cells. These events lead to increased pulmonary vascular and epithelial permeability, lung oedema, loss of surfactant, and atelectasis, all of which contribute to loss of aerated lung tissue. The clinical hallmarks are arterial hypoxemia and radiographic opacities associated with increased shunting, increased alveolar dead space, and decreased lung compliance. Based on the severity of hypoxaemia $^{1-3}$, ARDS is categorised into mild, moderate, and severe. Our target population of ARDS patients will be moderate to severe hypoxaemia categories defined based on either the PaO₂/FiO₂ ratio (P/F ratio) or the SpO₂/FiO₂ (S/F ratio). Moderate category is defined as P/F ratio between 100 - 200 or S/F ratio (if SpO₂≤97%) between 148 - 235. Severe is defined as P/F ratio between ≤ 100 or S/F ratio (if SpO₂≤97%) between ≤ 148 .

ARDS is a common and devastating acute critical illness.

An international, multicentre, prospective cohort study of 459 ICUs from 50 countries across 5 continents undergoing invasive mechanical (IMV) or non-invasive (NIV) ventilation reported a period prevalence of 10.4% of intensive care unit admissions. This equates to an estimated potential global burden of ARDS by World Bank region of around 1 to 5 in 10,000 per-year (across World Bank regions)⁴.

ARDS is a major cause of short-term mortality, and long-term morbidity and mortality.

The acute hospital mortality in ARDS increases with severity of hypoxaemia, with acute hospital mortality in excess of 40% in more severe illness. ARDS survivors also have exercise limitations, psychological sequelae, decreased physical quality of life, increased costs, and high use of health care services for up to 5 years after they recover from their acute illness⁴⁻⁶.

ARDS has significant resource implications for healthcare systems.

In the NHS, ARDS accounts for a considerable proportion of ICU resource use. Every year, over 120,000 patients are admitted to UK ICUs needing IMV and ~25% of IMV patients will have ARDS.

Severe ARDS patients have a median (inter-quartile range (IQR)) duration of mechanical ventilation of 9 (4-16) days, ICU length of stay of (LOS) of 11 (5-19) and hospital LOS of 16 (6-31) days⁴. Further, patients with ARDS utilise considerable ICU/hospital capacity and cost (Cost per NHS ICU bed-day = £1932; ward= £413; mean estimated cost of ICU stay based on a UK RCT involving ARDS patients⁷ was £26,857 (95 % CI £25,222–£28,491))⁸. Given the long-term sequalae described above, ARDS survivors continue to need primary care contact and ongoing rehabilitation in the community. The mean societal cost at 1 year exceeds £40K, and the total societal cost divided by the number of 1-year survivors is estimated to exceed £90K⁷.

1.1.2 Current management of ARDS patients (i.e., usual care for the trial)

The current management of ARDS (i.e., usual care) consists of optimising the diagnosis and treatment of underlying conditions, the deployment of supportive measures that minimise lung injury and the prevention of the consequences of critical illness with supportive care. Thus, the current ARDS management can be broadly divided into ventilatory management, and non-ventilatory management⁹¹⁰.

Ventilatory management of ARDS

In patients who require IMV, the use of low tidal volumes (<6 ml/kg ideal body weight) and limiting the airway pressures (plateau pressure <30 cmH2O) is the current recommendation⁹. The setting of positive end expiratory pressure (PEEP) during invasive mechanical ventilation is loosely linked to the inspired oxygen fraction (FiO2), with higher PEEP often used with more severe hypoxemia. In patients with more severe ARDS, prone position ventilation is recommended as part of usual care in the NHS setting.

Non-ventilatory management of ARDS

Patients who develop more severe hypoxaemia, often require sedation, and muscle relaxants to ensure adequate oxygenation. When all the above measures fail to maintain adequate levels of gas exchange, extracorporeal membrane oxygenation (ECMO) is provided in the specialist severe respiratory failure centres in the UK.

1.2 RATIONALE FOR STUDY

1.2.1 Justification of the trial

We recently conducted a systematic review to understand the up-to-date landscape of randomised clinical trials (RCTs) in ARDS¹¹. Despite 50 years of research, there are no recommended pharmacological therapies for all-cause ARDS¹².

Glucocorticoids are potent anti-inflammatory drugs, with a good risk benefit profile, and have therefore been tested previously in randomised clinical trials involving ARDS patients. The clinical effectiveness of glucocorticoids in all-cause ARDS, described in section 1.2.3 (i.e., ARDS 'not due to COVID-19') remains uncertain⁹.

DEXA-ARDS¹³, a multicentre RCT conducted in 17 ICUs in Spain, tested a 20 mg starting dose of dexamethasone (as dexamethasone sodium phosphate) in moderate-to-severe ARDS¹, i.e., three times higher than the dose shown to be effective in COVID-19¹⁴. It is important to note the following challenges about DEXA-ARDS RCT before accepting the conclusion that dexamethasone 20mg may benefit patients with all-cause ARDS¹³. The DEXA-ARDS trial stopped early after enrolling 88% of the planned sample size of 314 patients. The trial was powered for the primary outcome of ventilator-free days at 28 days. This short-term primary outcome does not capture the risk of delayed clinical deterioration requiring reintubation at ~180 days seen in the LaSRS Trial¹⁵. The potential long-term safety of glucocorticoid therapy was not reported in DEXA-ARDS trial, a clinically important evidence gap. It is also plausible that usual care provided in the NHS may differ from Spanish usual health care, as outcomes from critical illness are different between the two countries¹⁶.

Furthermore, there are safety concerns due to paucity of RCT data on the short-term as well as the longer-term adverse effects of short course glucocorticoids in this population 9.17. This clinical uncertainty of benefit and risk of harm is reflected in the current UK guidelines for ARDS management 19: 'The use of glucocorticoids in established ARDS should be the subject of a suitably powered, multicentre RCT with long-term follow-up (GRADE: research recommendation 9).'

Finally, our research question addresses - what is the role of glucocorticoids in all-cause early ARDS? – is one of the top priorities identified by NIHR-funded James Lind Alliance Intensive Care research Priority Setting Partnership as important to patients, carers and health professionals **It is the best way of preventing damage to the lungs of patients receiving respiratory support (ventilation)?

1.2.2 Role of glucocorticoids in ARDS

Systematic reviews and meta-analyses suggest glucocorticoids might be effective in reducing 28-day mortality in patients with all-cause ARDS (1098 patients in 9 RCTs, RR (95% CI) 0.75, 95% CI 0.59–0.94 in fixed effects model, and absolute risk reduction (ARR) (95% CI) 11.9(9.9–14.2%) (p<0.001); (I²=5.8%) (Figure-1)¹⁹⁻²¹. The study proposed here would be considerably larger than the current evidence base.

Steroids - Control -Control -Starting Total Events Total ratio (95% CI) Weight Dose Study Duration Methylprednisolone Bernard 1987 50 31 49 0.95 (0.50, 1.80) 11.35 Methylprednisolone 24 hours 30mg/Kg QDS 0.20 (0.03, 1.27) Methylprednisolone Meduri 1998 3.02 32 days 2mg/Kg Meduri 2007 63 12 28 0.56 (0.23, 1.34) 7.51 Methylprednisolone 28 days 1mg/Kg 9 18 0.07 (0.00, 1.57) Rezk 2013 3 2.37 Methylprednisolone 1mg/Kg 28 days 91 Steinberg 2016 26 89 1.02 (0.55, 1.90) 11.68 Methylprednisolone 2mg/Kg Subtotal (I-squared = 34.0%, p = 0.195) 0.77 (0.53, 1.12) 35.93 Hydrocotisone 92 7 days 50mg QDS Annane 2006 85 62 0.86 (0.53, 1.38) 21.44 Hydrocotisone Liu 2012 12 14 0.33 (0.06, 1.92) 2.81 Hydrocotisone 7 days 100mg TDS 98 Hydrocotisone 50ma QDS Tongvoo 2016 34 40 99 0.86 (0.50, 1.47) 16.95 7 days 0.82 (0.58, 1.16) Dexamethasone Villar 2020 29 138 0.58 (0.34, 0.96) 22.87 Dexamethasone 10 days 20mg daily Subtotal (I-squared = .%, p = .) 0.58 (0.34, 0.96) 22.87 Overall (I-squared = 5.8%, p = 0.387) 0.75 (0.59, 0.94) 100.00

Figure-1: Summary of evidence informing the estimated treatment effect

The main methodological findings of our and other systematic reviews 11,19,20 were that most were small RCTs with either surrogate or short-term mortality as primary outcomes. Most RCTs studied 'early' ARDS patients, i.e., randomised within 72 hours of ARDS onset, suffered from moderate risk of bias from lack of allocation concealment, blinding, and outcome ascertainment. Importantly, RCTs use different glucocorticoids, at different doses, for different durations adds uncertainty to this evidence. Therefore, glucocorticoids should not be used as standard of care (or usual care) currently in ARDS patients.

1.2.3 How did we choose the dosing regimen to test in the GuARDS Trial?

Amongst the different regimens reported in the literature, the dosing regimen used in the DEX-ARDS trial appears to be most promising ¹³. DEX-ARDS administered 20mg Dexamethasone sodium phosphate intravenously for days 1-5 and then 10mg intravenously for days 6-10. This study forms the evidence base for this study. The 60-day mortality was 15.3% lower in the dexamethasone group. We reason that dexamethasone at the proposed dose has the highest anti-inflammatory effects compared with other glucocorticoids. Dexamethasone will have pharmacological effects from day 1 that continue beyond the 10-day treatment regime. In pharmacokinetic simulations will maintain a high glucocorticoid

receptor occupancy (trough to peak: 50-90%)²², and will enable once daily dosing due to long biological half-life.

1.2.4 Hypothesis

Our primary hypothesis is that adult ICU patients with early ARDS (defined as within 72 hours from ARDS diagnosis), and moderate to severe hypoxaemia who are treated with dexamethasone plus usual care will have lower mortality at 60-days compared with those receiving usual care alone. Our rationale for the 'early' (defined as within 72 hours from ARDS diagnosis) treatment regime represents a balance between recruitment feasibility and biological rationale. Biological rationale is that glucocorticoids when administered at the early 'exudative' inflammatory phase, which occurs in the first 72 hours of ARDS onset will reduce inflammation, thereby preventing progressive lung oedema and lung damage¹².

1.2.5 Aim

Our aim is to conduct a multi-centre, parallel group, pragmatic RCT to investigate the clinical and cost effectiveness of dexamethasone plus usual care in patients with ARDS with moderate to severe hypoxaemia, compared with usual care of ARDS patients.

2. STUDY OBJECTIVES

2.1 OBJECTIVES

2.1.1 Primary Objective

To determine the clinical effectiveness of dexamethasone in patients with ARDS with moderate to severe hypoxaemia (referred to as patients with moderate to severe ARDS) on the primary outcome of 60-day mortality.

2.1.2 Secondary Objectives

To determine the clinical effectiveness of dexamethasone in moderate to severe ARDS on a range of clinically relevant secondary outcomes included within the CoVENT core outcome set (COS) for ventilation trials²³

To assess the cost-efficiency of dexamethasone plus usual care versus usual care alone in the treatment of ARDS, as per NICE reference case specifications modelled over 1, 3, and 5 year, and lifetime time horizons.

2.1.3 Exploratory Objectives

To collect blood samples to evaluate the biological mechanisms in patients with moderate to severe ARDS.

2.2 ENDPOINTS

2.2.1 Primary Endpoint

All-cause mortality at 60-days from randomisation.

2.2.2 Secondary Endpoints

Our proposed secondary outcomes (endpoints) are from the CoVENT core outcome set (COS) for ventilation rials²³. The timing of their assessments, measurement tools, and justification are summarised in Table 1.

Table-1: Secondary endpoints description

Outcome	Measurement tool or method	Rationale and justification
In-hospital		
First successful	Extubation is defined as free from	Defined as time from randomization
extubation	all tubes, endotracheal tube, and	until first successful extubation or
	tracheostomy. Success is defined	the patient's death occurs. We will
	as remaining free from tubes at 48	record the date/time of all periods of
	hrs. If discharged from hospital	ventilation up to day 60.
	before the 48-hr success period,	, , , ,
	assume extubation is successful.	
Duration of	Unassisted breathing defined as	Defined as time from randomization
mechanical	no inspiratory support (includes	until first successful unassisted
ventilation	time receiving invasive mechanical	breathing or the patient's death
	ventilation and non-invasive	occurs.
	ventilation) or extracorporeal lung	occuro.
	support. Success defined as	
	remaining to breathe unassisted at	
	48 hr.	
	Death prior to end of mechanical	
	ventilation or within the 48- hour	
	period after end of mechanical	
	ventilation is considered censored.	
Reintubation	All reintubation events with	The COS recommends reintubation
T Contradation	date/time to report the total	rates at 60-days. To capture the risk
	number of reintubations after a	of delayed reintubation 15 we will
	planned extubation in each group	collect this outcome for up to 180
	and the average number of	days from randomization, censored
	reintubation events/participant in	at hospital discharge).
	each group.	at nospital dissinal go).
Duration of ICU	Time from randomisation until	Included in relevant COS
and hospital stay	participant first leaves the relevant	
and moopher oray	facility or death	
60-days	,	
Heath Related	HRQoL will be measured using the	HRQoL is an important participant-
Quality of Life	EQ-5D at Baseline, 60 days and	reported outcome. EQ-5D is
(HRQoL)	180days. (www.euroqol.org).	recommended for health economic
,	, , , , , , , , , , , , , , , , , , , ,	evaluations.
Health service use	Rehospitalisation, Health service	Health service usage is data
since hospital	usage	required for health economic
discharge	3	analyses
90-days		-
Mortality	We will record the event date/time	We will also be able to estimate
,	of event, as well as date/time of	mortality at a priori defined time
	randomization to enable survival	point of 90-days, and 180-days.
	analysis.	
HRQoL	As described above	As described above
Health service use	As described above	As described above
since hospital		
discharge		
180-days		

Mortality	As described above.	As described above.
HRQoL	As described above	As described above
Health service use	As described above	As described above
since hospital		
discharge		

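### Reintubation is collected to day 180 to catch delayed events but is censored at hospital discharge, so it captures only those within the index stay

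*Protocol*

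**What the plan says.** Section 1.2.1 criticises the short-term primary outcome of the earlier dexamethasone trial because it "does not capture the risk of delayed clinical deterioration requiring reintubation at ~180 days", a risk it attributes to another steroid trial.

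Table 1 in section 2.2.2 takes this up in the Reintubation row. It notes that the core outcome set asks for "rates at 60-days. To capture the risk" of delayed reintubation, and adds that the trial will "collect this outcome for up to 180" days. The sentence closes by stating this limit in "days from randomization, censored" "at hospital discharge". The row asks for every reintubation with its date and time, and it sits in the in-hospital block of the table.

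The First successful extubation row of the same table sets another limit: it records all periods of "ventilation up to day 60".

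On length of stay, section 1.1.1 gives, for severe ARDS, a "hospital LOS of 16 (6-31) days".

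**The concern.** The row gives a reason for looking out to 180 days and, in the same sentence, a rule that ends observation for most participants much earlier. A participant discharged on day 25, readmitted and reintubated on day 70 falls inside the 180-day window and fits the stated purpose, but is not counted.

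This matters because delayed deterioration after steroids is part of the protocol's justification for a new trial. A low reintubation count labelled as 180-day data could be taken as reassurance about late harm during a period when few participants were under observation for it.

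The two recording limits in Table 1 add a practical problem. A site following the extubation row would stop recording ventilation periods at day 60. A site following the reintubation row would go on to day 180 for anyone still in hospital.

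**Working it through.** The protocol gives no figure to reproduce here. The check has two parts.

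**1. Is post-discharge intubation collected anywhere else?**

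- Reintubation row, Table 1: ends at hospital discharge.
- Extubation row, Table 1: ventilation periods to day 60.
- Table 3 (section 7.4): no reintubation row. Mechanical ventilation status is marked for randomisation, days 2-5, days 6-10 and ICU stay only.
- Section 11.2: adverse event recording ends at 21 days, death or ICU discharge, whichever comes first.
- Table 1 and sections 7.4, 8 and 8.3: follow-up at 60, 90 and 180 days and national linkage cover mortality, quality of life and health service use. Rehospitalisation is named; intubation is not.

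No part of the protocol records an intubation after discharge as such.

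**2. How much of the 180-day window is observed?**

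Input: hospital stay in severe ARDS, median 16 days, quartiles 6 and 31 (section 1.1.1).

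*Directly from the upper quartile:* 75% of stays have ended, by discharge or death, by day 31.

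*Beyond day 31 a tail must be assumed.* Log-normal, with P(stay > t) = 1 − Φ[(ln t − ln 16)/σ]:

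| σ taken from | σ | Day 60 | Day 180 |
|---|---|---|---|
| upper quartile: ln(31/16)/0.6745 | 0.981 | 8.9% | 0.7% |
| both quartiles: ln(31/6)/(2 × 0.6745) | 1.217 | 13.9% | 2.3% |
| lower quartile: ln(16/6)/0.6745 | 1.454 | 18.2% | 4.8% |

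Weibull, with P(stay > t) = exp[−(t/λ)^k]:

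| Fitted to | k | Day 60 | Day 180 |
|---|---|---|---|
| median and upper quartile: k = ln(ln 4/ln 2)/ln(31/16) | 1.048 | 6.3% | 0.02% |
| both quartiles: k = ln[ln 4/ln(4/3)]/ln(31/6) | 0.958 | 7.4% | 0.06% |

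No single fit is preferred. The log-normal through both quartiles, for example, puts 29% beyond day 31, where the stated quartile implies 25%. The range is 6-18% still in hospital at day 60 and 0.02-5% at day 180. Scaled to 1708 participants, the log-normal fits leave 152 to 310 in hospital at day 60 and 12 to 82 at day 180.

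**The case against.** **The scope is disclosed.** Table 1 and the Trial Summary both list reintubation under in-hospital outcomes, so censoring at discharge may be deliberate. That is a fair reading of the heading, but it does not rescue the sentence. If the outcome is meant to be in-hospital only, the claim that it captures delayed reintubation is what has to change.

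**Late harm is sought elsewhere.** Mortality, quality of life and rehospitalisation are followed to 180 days. The patient readmitted on day 70 should appear as a rehospitalisation, and as a death if the event is fatal. This stands, so it would be wrong to say that late harm is not looked for at all. What goes uncounted is the intubation itself.

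**Several stronger readings are tempting and are not supported.**

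- A reader might infer that the outcome cannot capture delayed reintubation. It can, during a prolonged index stay.
- A reader might infer that ventilation data for this outcome stop at day 60. That limit is in the extubation row, while the reintubation row sets 180 days. It is an unreconciled conflict, not a settled cut-off.
- A reader might turn one tail fit (13.9% in hospital at day 60) into a statement that at least 86% of participants are lost to observation. It is not a lower bound, since the fits range from 82% to 94% out of hospital, and it includes the dead. The protocol expects 40% control mortality at 60 days and an 8-point reduction, an average of (40 + 32)/2 = 36%. On that one fit, those alive but unobserved are about 86 − 40 = 46% to 86 − 36 = 50%.
- A reader might infer that the average number of events per participant favours the arm with more deaths. The protocol does not fix how death is handled in that comparison. Section 10.2 leaves secondary models general, and the detail belongs to the analysis plan, which is not at hand.

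**The size of the missed risk is unknown.** Section 1.2.1 does not say whether the delayed reintubations it cites occurred before or after discharge. This also stands: the documents show how much observation time is lost, not how many events.

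**Conclusion.** The concern holds as a contradiction within one secondary endpoint: the stated purpose runs to 180 days, while the censoring rule ends observation at the first hospital discharge. All reintubation on readmission is missed, so most of the period the rationale points to goes unobserved.

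The firm part of the size is that about 75% have left hospital or died by day 31. The day-60 and day-180 shares are illustrative. They rest on an assumed distribution shape, on severe-ARDS stay applied to a moderate-to-severe population, on stay counted from randomisation, and on deaths pooled with discharges. Under every fit the far end of the window is nearly empty.

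The day-60 and day-180 recording limits are a separate inconsistency and need reconciling. The text should be corrected because the outcome is tied to a stated justification for the trial.

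**What to change.** Either of two changes resolves it.

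1. **Keep the purpose.** Remove the censoring at hospital discharge. Ascertain intubation after discharge through the resource-use calls already scheduled at 60, 90 and 180 days and the hospital linkage already planned. State one recording limit for ventilation and reintubation that is consistent across the rows of Table 1, and add reintubation to Table 3. The cost is an added question on each call and a request for procedure information in the linkage. The downside is that post-discharge events will be ascertained and dated less exactly, since they rely on patient or proxy recall, and linkage fields may vary between the four nations.

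2. **Keep the censoring.** Define the outcome as reintubation during the index admission, delete the statement that it captures delayed reintubation to 180 days, and reconcile the day-60 and day-180 limits. This costs only a wording change, but the trial then gives no direct evidence on reintubation after discharge, and its report should say so.
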